6.6.1.3 Sensitivity Analysis

The primary analysis of ORR will be based on the safety population. Sensitivity analyses for ORR include, but not limited to:

1. ORR assessed by investigator will be analyzed using the ITT population.
2. ORR assessed by investigator will be analyzed using the per protocol population if patients excluded due to major protocol deviation are deemed to have significant impact on the analysis of primary endpoints.
3. ORR assessed by investigator will be analyzed using the response-evaluable population.

For the primary endpoint ORR, subgroup analysis will be performed in the following selected subgroups and presented using forest plot within each treatment arm. Additional subgroups of clinical interest may also be considered if data permits, but not required by this SAP.

Subgroups	Categories
Age group (at screening)	18 to <65; 65 to < 75; ≥ 75
Gender	Male; female
Race	White; Black; Asian; Other
Type of myeloma	IgA; IgG; light chain only
Cytogenetics risk	High risk [defined as 17p-, t(4;14) and/or t(14;16)]; complementary standard risk (non-high risk)
R-ISS	I/II; III
ISS	I/II; III

Extramedullary disease	Yes; no
Prior treatment	Naïve to anti-CD38; sensitive (non-refractory) to anti-CD38
Number of prior lines of therapy	1; 2/3
Transplant status	Transplanted; Non-transplanted

If the percentage of subjects is small within a particular subgroup, then the subgroup categories may be refined prior to the database lock.

6.6.2 Secondary Endpoints Analysis

6.6.2.1 Phase 1 dose escalation

For the phase 1 dose escalation, secondary efficacy endpoints include ORR, DOR, PFS, OS, MRD[-] CR rate, MRD[-] rate, and duration of MRD negativity.

ORR

ORR is defined in Section [6.6.1.1](#).

The analysis of ORR will be based on the response-evaluable population.

ORR will be summarized by frequencies, percentages, and 2-sided 95% exact binomial CIs.

DOR

DOR is defined as the time from the date of first documentation of a confirmed PR or better to the date of first documentation of confirmed progressive disease or death due to any cause, whichever occurs first. Responders without documentation of confirmed progressive disease or death will be censored at the date of last adequate disease assessment. The censoring rule for DOR is the same as for PFS. Please refer to [Table 1](#) in Section [6.6.2.2](#) for the detailed censoring rules.

DOR (months) = (earliest date of progression or death or censor – date of confirmed response + 1)/30.4375

The analysis of DOR will only include confirmed responders (PR or better) based on the safety population.

DOR will be summarized using KM method. The K-M curves, the 25th, 50th (median) and 75th percentiles, alone with associated 2-sided 95% CIs based on Brookmeyer and Crowley method, and the K-M probability estimates with 95% CIs at 3, 6, 9 and 12 months (or later time points if applicable) will be presented. The number of patients with events along with the type of events (death or progressive disease) and the number of patients censored will be summarized.

PFS

PFS is defined as the time from the date of the first dose administration of any study drug to the first documentation of confirmed progressive disease or death due to any cause, whichever occurs first. Patients without documentation of confirmed progressive disease or death will be censored at the date of last adequate disease assessment prior to the date of initiation of subsequent anti-cancer therapy. Patients with no post baseline response assessment will be censored on day 1 unless patient died without extended loss-to-follow-up time. Determination of dates of PFS event and date for censoring is summarized in [Table 1](#) as follows.

Table 1: PFS Event and Censoring Method

Scenarios	Event date/censoring date	Event status
No (or inadequate) baseline tumor assessments ¹	Date of the first dose	Censored
No post-baseline assessments	Date of the first dose	Censored
Confirmed progression documented without extended loss-to-follow-up time (two or more missed cycles)	Date of assessment of the earliest date of the confirmed progression	PFS Event
No confirmed progression or death	Date of last adequate disease assessment ²	Censored
Subsequent anti-cancer therapy started (before documented confirmed progression or death) ³	Date of last adequate disease assessment ² (prior to the initiation of the subsequent anti-cancer therapy)	Censored
Death without extended loss-to-follow-up time	Death date	PFS Event
Death or progression after an extended loss-to-follow-up time (two or more missed cycles)	Date of last adequate disease assessment ² (prior to missed assessments)	Censored

1. Adequate baseline assessment is defined as at baseline, a patient has at least one of the following measurements:
 - a) Serum M-protein $\geq 0.5\text{g/dL}$ ($\geq 500\text{ mg/dL}$) or
 - b) Urine M-protein $\geq 200\text{ mg/24 hours}$ or
 - c) Serum FLC assay: Involved FLC level $\geq 10\text{ mg/dL}$ ($\geq 100\text{ mg/L}$) and an abnormal serum FLC ratio (<0.26 or >1.65)
2. An adequate disease assessment is defined as an assessment where the investigator determined response is sCR, CR, VGPR, PR, MR, or SD prior to a subsequent anti-cancer therapy. An unconfirmed PD assessment is also considered as an adequate assessment.
3. If PD or death and the subsequent anti-cancer therapy occur on the same day, it is assumed that the progression or death was documented first (e.g., event status is an event, and the date of event is the date of progression or death). If the subsequent anti-cancer therapy is initiated prior to any adequate assessment, censoring date should be the date of the first dose.

PFS (months) = (earliest date of progression or death or censor – date of first dose + 1)/30.4375.

The analysis of PFS will be based on the safety population.

PFS will be summarized using KM method. The K-M curves, the 25th, 50th (median) and 75th percentiles, alone with associated 2-sided 95% CIs based on Brookmeyer and Crowley method, and the K-M probability estimates with 95% CIs at 3, 6, 9 and 12 months (or later time points if applicable) will be presented. The number of patients with events along with the type of events (death or progressive disease) and the number of patients censored will be summarized. The PFS follow-up time will be summarized and reported using the inverse KM methods.

OS

OS is defined as the time from the date of first dose administration of any study drug to the date of death from any cause. Patients without documentation of death at the time of analysis will be censored at the date last known to be alive.

OS (months) = (date of death or censor – date of first dose + 1)/30.4375.

The analysis of OS will be based on the safety population.

OS will be summarized using KM method. The K-M curves, the 25th, 50th (median) and 75th percentiles, alone with associated 2-sided 95% CIs based on Brookmeyer and Crowley method, and the K-M probability estimates with 95% CIs at 3, 6, 9 and 12 months (or later time points if applicable) will be presented. The number of patients with events and the number of patients censored will be summarized. The OS follow-up time will be summarized and reported using the inverse KM method.

MRD[-] CR Rate

MRD[-] CR rate is defined as the proportion of patients who have achieved confirmed CR assessed by the investigator and MRD[-] status using a threshold of 10^{-5} .

The analysis of MRD[-] CR rate will be based on the response-evaluable population.

MRD[-] CR rate will be summarized by frequencies, percentages, and 2-sided 95% exact binomial CIs.

MRD[-] Rate

MRD[-] rate is defined as the proportion of patients who have achieved MRD[-] status using a threshold of 10^{-5} .

The analysis of MRD[-] rate will be based on the response-evaluable population.

MRD[-] rate will be summarized by frequencies, percentages, and 2-sided 95% exact binomial CIs.

Duration of MRD negativity

Duration of MRD negativity is defined as the time from the date of first documentation of MRD negativity to the first documentation of MRD positivity or confirmed progressive disease, or death due to any cause, whichever occurs first. Patients without documentation of MRD positivity or confirmed progressive disease will be censored at the date last known to be MRD negative.

Duration of MRD negativity (months) = (earliest date of MRD positivity or progression or death or censor – date of MRD negativity + 1)/30.4375.

The analysis of duration of MRD negativity will include only patients who have achieved MRD negativity with a threshold of 10^{-5} based on the safety population.

If data permits, duration of MRD negativity will be summarized using KM method. Otherwise, a listing will be generated.

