Censoring rule would follow [Table 1](#) except for replacing “the date of first dose” with “the date of randomization”.

PFS (months) = (earliest date of progression or death or censor – date of randomization + 1)/30.4375.

PFS would be analyzed in the same way as described in Section [6.6.2.1](#) based on the ITT population. Sensitivity analysis based on the safety population may also be provided.

OS

OS is defined as the time from the date of randomization to the date of death due to any cause.

OS (months) = (date of death or censor – date of randomization + 1)/30.4375.

OS would be analyzed in the same way as described in Section 6.6.2.1 based on the ITT population. Sensitivity analysis based on the safety population will also be provided.

MRD[-] CR rate

MRD[-] CR rate is defined in Section 6.6.2.1 and will be analyzed in the same way based on the safety population.

MRD[-] rate

MRD[-] rate is defined in Section 6.6.2.1 and will be analyzed in the same way based on the safety population.

Duration of MRD negativity

Duration of MRD negativity is defined in Section 6.6.2.1 and will be analyzed in the same way based on the safety population.

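### SAP Table 1 censors at first dose, without the death exception given in the text, when the baseline is missing or inadequate or there is no post-baseline assessment, so an early death can match both a censoring row and an event row

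*SAP*

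**What the plan says.** **Phase 1 text (SAP 6.6.2.1, PFS).** "Patients with no post baseline response assessment will be censored on day 1 unless patient died without extended loss-to-follow-up time". The next sentence introduces the table: "Determination of dates of PFS event and date for censoring is summarized in" Table 1.

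**Table 1.**
- Row 1, no or inadequate baseline assessment: date of first dose, censored. Footnote 1 defines adequacy by measurable-disease thresholds.
- Row 2, "No post-baseline assessments": date of first dose, censored.
- Death row, "Death without extended loss-to-follow-up time": death date, PFS event. It does not require an earlier assessment.
- Last row, death or progression after two or more missed cycles: censored at the last adequate assessment before the gap.
- Subsequent-therapy row and footnote 3: censored at the last adequate assessment before the new therapy, or at first dose if there was none.

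Nothing says which row applies when a patient meets two.

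**Phase 2a (SAP 6.6.2.2, PFS).** PFS runs from randomization to confirmed progression or death from any cause, in the ITT population. "Censoring rule would follow" Table 1, with only the origin date changed. The section then adds: "PFS would be analyzed in the same way as described in Section" 6.6.2.1.

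**Protocol 13.1.3.2.1 and 13.1.3.2.2.** In both phases death from any cause is a PFS event, and censoring applies only to patients without documented confirmed progression or death.

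**The concern.** The text and the table give different rules for the same patient. Someone who dies before any post-baseline assessment is an event under the Phase 1 sentence and the death row, but is censored at time zero under row 2. If the baseline is also missing or below the thresholds, row 1 censors too, and the exception in the text does not mention that situation.

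These are the shortest PFS times in the study. Censoring them at the origin removes them from the risk set before they can count, so an error here can only push the PFS curve upward. Analysis programs are often specified from a censoring table rather than from the paragraph above it, so the table should carry the whole rule.

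**Working it through.** **Which rows an early death meets**

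1. The first scheduled investigator response assessment is Cycle 2 Day 1, with 28-day cycles (protocol Appendix A, Schedule of Events Tables 1 and 3).
2. Extended loss to follow-up means two or more missed cycles (Table 1). A patient who dies before Cycle 2 Day 1 cannot have missed two cycles, so the death row applies.
3. The same patient has no post-baseline assessment, so row 2 applies. Row 1 applies as well if the baseline is missing or inadequate.

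| Death before Cycle 2 Day 1 | Censoring row met | Event row met | Resolved elsewhere? |
|---|---|---|---|
| Phase 1, adequate baseline | Row 2 | Death row | Yes: the sentence before the table makes it an event |
| Phase 1, missing or inadequate baseline | Rows 1 and 2 | Death row | Row 2 yes; row 1 no |
| Phase 2a, either baseline | Same rows, dated at randomization | Death row | Only through the general reference to 6.6.2.1 and the PFS definition |

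**Size**

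The documents give no PFS estimate, event target or early-death rate, so there is no planned figure to reproduce. The arm size of about 20 is from SAP Section 4.0. The number of early deaths, k, is an assumption. Assume also no other event or censoring by Day 28.

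- Deaths counted as events: K-M PFS at Day 28 = (20 − k)/20.
- Deaths censored at the origin: the remaining 20 − k patients are all event-free, so K-M PFS = 1.00.

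| k (assumed) | As events | Censored | Difference |
|---|---|---|---|
| 1 | 19/20 = 95% | 100% | 5 points |
| 2 | 18/20 = 90% | 100% | 10 points |
| 3 | 17/20 = 85% | 100% | 15 points |

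The SAP's named K-M time points start at 3 months, where the gap is somewhat smaller. Assume exponential PFS with median m months in the other patients and no other censoring, so S(3) = 2^(−3/m). The estimate is S(3) if the early deaths are censored and S(3) × (20 − k)/20 if they are events.

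- m = 12, k = 2: S(3) = 0.841 against 0.841 × 0.90 = 0.757. The median is 12.0 against 12 × log2(0.90/0.50) = 10.2 months.
- m from 6 to 18: the 3-month difference is 3.5 to 4.5 points for k = 1, 7.1 to 8.9 for k = 2, and 10.6 to 13.4 for k = 3.

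The chance that an arm of 20 has at least one such death is 1 − (1 − q)^20. For assumed risks q of 2%, 5% and 10% this is 33%, 64% and 88%.

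**The case against.** The strongest answer is that the plan does not intend to censor early deaths. The exception stands immediately before the table, the table is introduced as a summary of what precedes it, and both the SAP and the protocol define death from any cause as a PFS event. For row 2 in Phase 1 this settles the status, and that part of the objection stands in full.

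For Phase 2a, the reference back to Section 6.6.2.1 reaches the section that holds the exception. That is a fair reading. But the reference concerns how PFS is analysed and could mean only the K-M presentation, whereas the sentence that deals with censoring cites Table 1 and changes nothing except the origin date. The exception is also worded in terms of Day 1, which SAP 6.1.1.1 ties to the first dose, while the Phase 2a ITT population can include patients who were never dosed.

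Row 1 may be nearly empty, because footnote 1 uses the same thresholds as inclusion criterion 3. That limits how often it matters but does not remove it. SAP 6.1 takes baseline as the last value before first dose, and the Schedule of Events repeats M-protein and free light chain at Cycle 1 Day 1 when the screening sample is more than 7 days old. A patient measurable at screening could therefore be below threshold at baseline.

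A slip would also leave traces: the SAP reports numbers of events and censored patients, lists all deaths, and counts every death in OS.

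**Conclusion.** The point holds as a conflict between stated rules that needs correcting, not as a biased analysis. Rows 1 and 2 lack the death exception and no precedence is stated. In Phase 1 the text repairs row 2 but not row 1. In Phase 2a the exception is not repeated in the censoring rule and has to be inferred.

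A reader might infer that the plan censors every patient without a post-baseline assessment, or that Phase 2a PFS is governed by the table alone. The documents support neither: the Phase 1 text exempts these deaths, and the Phase 2a section refers back to 6.6.2.1 and counts any death as an event. Nor do they say that rows apply from the top down, so an upward bias is a risk of literal programming rather than the plan's rule.

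That risk is 5 points of Day-28 PFS per early death in an arm of 20. The direction is certain; the number of deaths, and the medians behind the 3-month figures, are assumptions. PFS is secondary and descriptive, with no hypothesis test or comparison between dose levels, so no error rate or sample size is affected. The protocol history (Appendix G) records a sponsor decision not to proceed to Phase 2a. The Phase 1 gap in row 1 does not depend on that decision.

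**What to change.** Amend Table 1 as follows:

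- Restrict rows 1 and 2 to patients to whom the row "Death without extended loss-to-follow-up time" does not apply, so that such deaths are events at the death date.
- Keep censoring at Day 1 (randomization date in Phase 2a) for a patient with no post-baseline assessment who dies after an extended loss to follow-up. Simply excluding all deaths from row 2 would move this patient to the last row, whose censoring date, the last adequate assessment, does not exist.
- Leave the subsequent-therapy row and footnote 3 unchanged and ranked ahead of the death row. An unqualified rule that death takes precedence would override them.
- State in SAP 6.6.2.2 that the same exception applies to Phase 2a PFS.

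The cost is two table cells, a line on precedence and one sentence for Phase 2a. No data collection, sample size or other endpoint definition changes.

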#### 8.6.1.2 Criteria for Beginning or Delaying a Subsequent Treatment Cycle

Treatment with modakafusp alfa will use a cycle length of 28 days. For a new cycle of treatment to begin, the patient must meet the following criteria:

- ANC  $\geq 1000/\text{mm}^3$ . Granulocyte-colony stimulating factor can be used to reach this level.
- Platelet count must be  $\geq 50,000/\text{mm}^3$ . Platelet transfusion can be applied any time clinically indicated but should not be applied only for the purpose of meeting the treatment criterion of platelet count.

For therapy to resume, toxicity considered to be related to treatment with modakafusp alfa must have resolved to Grade  $\leq 1$  or baseline (Grade 2 for neutrophil and platelets), or to a level considered acceptable by the physician. If the above-cited criteria for retreatment are not met for a patient, initiation of the next cycle of treatment should be delayed for 1 week. At the end of that week, the patient should be re-evaluated to determine whether the criteria for retreatment criteria have been met.

If there is a delay of a subsequent cycle longer than 2 weeks because of a related AE, the patient may be withdrawn from treatment unless there is clinical benefit as assessed by the investigator, with agreement by the sponsor.

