#### 9.5.13.10 *Central Laboratory Evaluations*

##### BMA for MRD

For all patients, a BMA for MRD sample to determine rate and duration of MRD negativity should be collected at screening at the same time as the BMA and biopsy procedure is performed for local disease assessment purposes. Additionally, when a CR is suspected based on laboratory values, per routine clinical practice ([Appendix E](#)), a BMA should be drawn for local disease assessment and central analysis of MRD. Additionally for patients with a confirmed CR, BMAs for MRD should be collected at 6, 12, and 24 months following CR confirmation. If a patient has an MRD[-] result for any of the on-treatment assessments, this will trigger yearly evaluations of MRD, until the patient progresses. However, if a patient does not have an MRD[-] result for any of the planned on-treatment assessments, no additional BMA for MRD will be required. These evaluations will be performed at a central laboratory.

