## **9.11 Posttreatment Follow-up Assessments (PFS and OS)**

Patients who stop treatment for any reason other than progressive disease will continue to have PFS visits. The PFS visits should occur every 4 weeks from the EOT until the occurrence of progression, death, the start of subsequent systemic antineoplastic therapy, study termination, whichever occurs first. OS follow-up continues every 12 weeks until death, study termination, or patient withdrawal. Imaging tests for patients with extramedullary disease should be performed every 12 weeks or if new symptoms suggest progressive disease.

See the SOE ([Appendix A](#)) for appropriate assessments during follow-up.

NOTE: Treatment-related SAEs must be reported to the Global Pharmacovigilance department or designee. This includes deaths that the investigator considers related to study drug that occur during the posttreatment follow-up. Refer to Section [10.0](#) for details regarding definitions, documentation, and reporting of SAEs.

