### **DOR, PFS, OS, and Duration of MRD Negativity**

DOR is defined as the time from the date of first documentation of a confirmed PR or better to the date of first documentation of confirmed progressive disease or death due to any cause, whichever occurs first. DOR will be calculated for confirmed responders only (PR or better). Responders without documentation of confirmed progressive disease or death will be censored at the date of last adequate disease assessment.

PFS is defined as the time from the date of the first dose administration of any study drug to the first documentation of confirmed progressive disease or death due to any cause, whichever occurs first. Patients without documentation of confirmed progressive disease or death will be censored at the date of last adequate disease assessment. The analysis will be based on the safety population.

OS is defined as the time from the date of the first dose administration of any study drug to the documentation of death due to any cause. Patients without documentation of death at the time of analysis will be censored at the date last known to be alive. The analysis will be based on the safety population.

Duration of MRD negativity for patients achieving MRD negativity is defined as the time from the date of first documentation of MRD negativity to the first documentation of MRD positivity or confirmed progressive disease, whichever occurs first. It will be calculated for patients achieving MRD negativity only. Patients without documentation of MRD positivity or confirmed progressive disease will be censored at the date last known to be MRD negativity.

For these endpoints, K-M survival curves and K-M medians (if estimable), together with 95% CIs, may be calculated if appropriate.

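### Duration of MRD negativity: event-free patients are censored at their last marrow test while later progression still counts, which biases the Kaplan-Meier curve downward wherever follow-up ends between tests

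*SAP*

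**What the plan says.** **Events.** SAP 6.6.2.1 ends the duration at "first documentation of MRD positivity or confirmed progressive disease, or death due to any cause, whichever occurs first". Protocol 13.1.3.2.1 names MRD positivity and confirmed progression only, without death.

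**Censoring.** The SAP states: "Patients without documentation of MRD positivity or confirmed progressive disease will be censored at the date last known to be MRD negative". The protocol's sentence is the same in substance: "Patients without documentation of MRD positivity or confirmed progressive disease will be censored at the date last known to be MRD negativity". SAP 6.6.2.2 and protocol 13.1.3.2.2 carry the definition into phase 2a.

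**How MRD status is known.** Under protocol 9.5.13.10 a marrow sample is taken when CR is suspected. After that, "BMAs for MRD should be collected at 6, 12, and 24 months following CR confirmation", and a negative on-treatment result means that "this will trigger yearly evaluations of MRD, until the patient progresses".

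**How progression is known.** The schedules of events place the investigator's assessment on Day 1 of each cycle, and "Treatment with modakafusp alfa will use a cycle length of 28 days". After treatment, "The PFS visits should occur every 4 weeks from the EOT until the occurrence of progression". For PFS, SAP Table 1 dates a progression event at: "Date of assessment of the earliest date of the confirmed progression".

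**Analysis.** The SAP uses Kaplan-Meier if the data permit and otherwise a listing. The protocol makes Kaplan-Meier optional in phase 1 but plans curves and medians for each arm in phase 2a.

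**The concern.** The two ways of leaving the risk set run on different clocks. A patient with a negative test at month 12 who progresses at month 20 contributes 20 months. An otherwise identical patient who is still progression-free at month 23 is sent back to month 12. Between tests a patient can be seen to fail but cannot be seen not to fail, so the time at risk after the last test comes only from those who fail. Kaplan-Meier needs censoring that carries no information about the event to come, and this rule breaks that condition in a known direction: downward.

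The endpoint is secondary in both phases. At stake is a reported curve and median that could make MRD negativity look much shorter than it is. In phase 2a the two dose arms could also be distorted to different degrees if their follow-up or number of progressions differed. SAP 6.6.2 contains no sensitivity analysis that would reveal this.

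**Working it through.** The documents give no planning figure for this endpoint, so there is none to reproduce. The check has three steps. Time is counted from first MRD negativity, taken for simplicity as the date of CR confirmation.

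**1. Worked example.** Ten MRD-negative patients: two progress, at months 18 and 20. The other eight are progression-free at month 23 and had their last MRD test at month 12. The estimator is S(t) = product over event times of (1 − d/n), with d events among n at risk.

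- Written rule: the eight leave at month 12. Month 18: 1 − 1/2 = 50%. Month 20: 50% × (1 − 1/1) = 0%.
- Censoring at the month-23 disease assessment: month 18: 1 − 1/10 = 90%. Month 20: 90% × (1 − 1/9) = 80%.

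**2. Same patients, longer follow-up.** Suppose the eight have also had a negative month-24 test. They are then at risk at months 18 and 20 under either rule, and both rules give 90% and 80%. The bias arises only from follow-up that ends inside a gap.

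**3. Simulation for size.**

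- From the protocol: MRD tests at 0, 6, 12, 24, 36 and 48 months; progression dated at 28-day visits.
- Assumed: exponential progression with a median of 24 or 36 months; no MRD relapse and no deaths; follow-up from first MRD negativity uniform over the range shown.
- Check on the true values: 0.5^(18/24) = 59.5% and 0.5^(18/36) = 70.7% at month 18. Dating progression at visits raises these slightly.

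| Follow-up (months) | Progression median | Quantity | Written rule | Last disease assessment | True |
|---|---|---|---|---|---|
| 12–24 | 24 | month 12 | 71% | 71% | 71% |
| 12–24 | 24 | month 18 | about 18% | 60% | 60% |
| 12–24 | 36 | month 12 | 79% | 79% | 79% |
| 12–24 | 36 | month 18 | 20% | 71% | 71% |
| 30–48 | 36 | month 24 | 63% | 63% | 63% |
| 30–48 | 36 | month 30 | 54% | 57% | 57% |
| 30–48 | 36 | median | 33 months | 37 months | 37 months |

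Variations, each on assumed inputs:

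- Follow-up 6–18 months, progression median 36: month-18 estimate 0% against about 72%.
- MRD tests after the first moved one month later, to allow for the delay to CR confirmation (follow-up 12–24 months): month-18 estimates of about 20% and 23% instead of 18% and 20%.
- MRD relapse added with a 36-month median (progression median 36, follow-up 12–24 months, tests moved one month): 17% against 55% at month 18.
- MRD relapse with a 24-month median, progression median 36, follow-up 30–48 months: median 18.4 months under both rules and in truth.
- Eight MRD-negative patients (progression median 36, follow-up 12–24 months, tests moved one month): the curve reaches zero in 42% of simulated trials under the written rule and in 4% when censoring at the last disease assessment.

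**The case against.** **MRD status after the last test is unknown, so stopping there is cautious.** That would be coherent if progression and death after that test were also ignored. Both documents count later progression, and the SAP counts later death. The caution is applied only to patients who are doing well.

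**The planned horizon is long.** Protocol 6.3.2 places the final analysis after all patients have completed assessments, and 6.3.4 gives about 60 months in total with 12 to 18 months of enrolment. Patients would then have between 60 − 18 = 42 and 60 months from entry. If first MRD negativity is assumed to come 12 months after entry, that leaves 30 to 48 months, where only the tail is affected. This stands, and it limits the size. The severe figures need a data cutoff within about 6 to 24 months of first MRD negativity, and the documents set no date for one.

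**A listing may replace the curve.** This also stands. The SAP allows it when data are sparse, which is realistic with about 18 patients in phase 1. The protocol's phase 2a text has no such condition.

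**The endpoint is descriptive.** SAP 3.1 to 3.3 set no hypotheses, decision rules or multiplicity adjustment. No formal conclusion depends on it.

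A reader might infer that the curve is biased in every gap between tests, or that it collapses in general. The documents do not support that. Patients who go on to another test stay at risk throughout the gap, and in the 12–24 month simulation the month-12 estimates are unbiased. The risk set loses all its event-free patients only after the last MRD test that anyone has reached.

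**Conclusion.** The censoring rule is wrong as written in both documents. It makes censoring depend on outcome and pulls the Kaplan-Meier estimate down in any gap between MRD tests in which follow-up ends. The mechanism follows from the text alone and needs no assumption.

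The size does rest on assumptions. With exponential progression (median 24 to 36 months), no MRD relapse and 12 to 24 months of follow-up, the month-18 estimate is 40 to 50 percentage points too low. With 30 to 48 months and a progression median of 36, the error is about 3 points at month 30 and about 4 months in the median. A general claim of a collapsing curve goes too far; the severe form is tied to an early cutoff. The point matters only if Kaplan-Meier estimates are produced. Because the endpoint is secondary and descriptive and the correction is cheap, it should be corrected before analysis, but it does not threaten the trial's primary conclusions.

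**What to change.** 1. **Settle death first.** The SAP counts it as an event but omits it from its censoring sentence; the protocol does not count it. State one rule in both documents.
2. **Replace the censoring sentence** in SAP 6.6.2.1 and protocol 13.1.3.2.1. Patients with no MRD positivity, no confirmed progression and (if death is made an event) no death are censored at the last adequate disease assessment before any subsequent anti-cancer therapy, following SAP Table 1. The SAP already uses that rule for PFS, DOR, duration of clinical benefit and duration of disease control.
3. **List each patient's last MRD test date**, so that readers can see how much of the duration rests on tested negativity.
4. **Sensitivity analysis, if wanted.** Censoring at the last MRD test can be kept only if progression and death after that test are also disregarded.

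The cost is one sentence in each document and a listing; no new data are needed. The downside is that MRD conversions not yet detected are credited as negative until the next scheduled test, which can be about 12 months in the later gaps.
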